#### 4.3.2. Secondary outcome models

Secondary abstinence outcomes will be assessed in the ITT population, other secondary outcomes in the completers and the ITT population. GLMM will be used to assess the difference in outcomes at follow up between treatment groups or changes from baseline.

All single endpoint outcomes will include a normally distributed random intercept for site (on the scale of the canonical link function for the specific distribution family) and treatment group as a fixed effect with a non informative prior for the treatment effect. The random intercept will be modelled from a normal distribution with mean 0 and a hierarchical variance parameter that is distributed as a half Student-T of 3 degrees of freedom.

For outcomes with multiple time points, the models will additionally include participant id as a random intercept, and parameters for time with an interaction between time and treatment group as fixed effects, all on the scale of the canonical link function for the specific distribution family. Non-informative priors will be used for fixed effects. Participant id

random intercept will be modelled from a multivariate normal distribution with mean 0 and covariance matrix with a non-informative prior (LKJ-Correlation and half Cauchy priors implemented in the brms R package).

A GLMM with a binomial distribution and logit link function will be used to model abstinence outcomes (biochemically verified 7-month continuous abstinence, self-reported 30 day and 7 day point prevalence, abstinence at 3 and 9 months).

Number of cigarettes smoked per day will be compared at each time point using a GLMM with a negative-binomial distribution and log link function. Percentage reduction of at least 50% in the number of cigarettes smoked per day will be assessed with GLMM with a binomial distribution and logit link function.

Craving scores and relapse episodes will be compared using a GLMM with multinomial distribution and a cumulative logit link function, or binomial distribution and logit link depending on the distribution of responses.

Withdrawal scores will be compared using a GLMM with normal distribution and identity link function.

Abstinence from all nicotine/ tobacco products will be modelled using GLMM with a binomial distribution and logit link function.

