#### **2.2.2. Secondary objectives**

Additional secondary objectives are to compare participants in the VNP + Quitline to those in the NRT + Quitline group on:

- i) Biochemically verified 7-month continuous abstinence at month 9
- ii) 30-day point prevalence abstinence at months 3 and 9
- iii) Reduction in cigarettes smoked per day at months 3 and 9
- iv) Reduction in strength and urges to smoke tobacco at months 3 and 9
- v) Reduction in withdrawal symptoms at months 3 and 9
- vi) Relapse episodes to smoking at months 3 and 9

Other objectives involve:

- i) Assessing treatment adherence (duration/ use of products/ reasons for non-use/ engagement with telephone counselling) compared by treatment group
- ii) Assess attitudes/ acceptability of the provided interventions
- iii) Use of additional pharmacotherapies, visits to GPs, and use of print and online materials
- iv) Assess provided interventions on mood

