#### 4.2.6. Summaries of the posterior distribution

**Posterior mean:** The mean of the converged posterior distribution for the parameter reflecting the between group differences (either absolute or relative) will be presented as the point estimate to 2 decimal places

**Intervals:** 95% credible intervals will be calculated using the highest posterior density (HPD) method and presented to 2 decimal places.

**Probability of direction:** The one-sided probability that the difference between treatment and control is greater than zero will be presented (representing a beneficial treatment effect). This is calculated as the proportion of posterior samples that are of sign that is favorable to the intervention (either +’ve or -’ve)

**Bayes Factors:** The relative evidence of a treatment effect compared to no treatment effect will be calculated. The marginal likelihood of models with and without the treatment effect will be calculated using a bridge sampler as implemented in the brms R package. The ratio of these likelihoods is the Bayes factor. A Bayes factor greater than 1 indicates there is more evidence the treatment is effective compared to no treatment effect. Bayes factor categories can be interpreted as substantial (3.2 to 10), strong (10 to 32), very strong (32 to 100), decisive (>100).

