### 4.3. Statistical models

#### 4.3.1. Primary outcome model

The primary outcome of interest will be assessed in the ITT population using a generalized linear mixed model (GLMM) with logit link function including a random intercept for site and treatment group as a fixed effect. Priors on the treatment parameter (difference in log odds between treatment arms) will be non informative and a power prior (normal distribution) based on previously published data will be used in the sensitive analysis. The random intercept will be modelled on the log-odds scale and assumed distributed as a normal distribution with mean 0 and variance assumed to be distributed from as a half Student-T of 3 degrees of freedom.

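### For abstinence measured at months 3 and 9, the planned participant-intercept logit yields a subject-specific effect that lies further from the null than the difference between the randomised groups and is not on the primary's scale

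*SAP*

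**What the plan says.** - **Repeated outcomes (SAP 4.3.2).** "For outcomes with multiple time points, the models will additionally include participant id as a random intercept, and parameters for time", with a time-by-treatment interaction, all on the link scale. The participant effect is normal with a "covariance matrix with a non-informative prior (LKJ-Correlation and half Cauchy priors implemented in the brms R package"). The scale of the half-Cauchy is not given.
- **Which outcomes this reaches (SAP 4.3.2 and 2.2.2).** "A GLMM with a binomial distribution and logit link function will be used to model abstinence outcomes", and the list that follows includes "self-reported 30 day and 7 day point prevalence, abstinence at 3 and 9 months". The secondary objectives likewise set "30-day point prevalence abstinence at months 3 and 9".
- **Primary (SAP 4.3.1).** A logit model at one time point, "including a random intercept for site and treatment group as a fixed effect". Its treatment parameter is the "difference in log odds between treatment arms". The biochemically verified outcome is also a single endpoint, so it has the site intercept and no participant intercept.
- **Reporting (SAP 4.2.6).** The posterior mean "for the parameter reflecting the between group differences (either absolute or relative) will be presented as the point estimate". This rule covers primary and secondary outcomes alike. Nothing in the SAP describes averaging over the participant effect, or says whether effects are conditional or population-averaged.

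**The concern.** In a logit model with a participant intercept, the treatment coefficient compares two people who share the same latent intercept. The odds ratio is non-collapsible, so this is not the odds ratio between the randomised groups. If there is an effect and the participant standard deviation (SD) exceeds zero, the conditional value is further from 1, and the gap grows with the SD.

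The SAP would therefore report two different quantities under one description: a nearly population-averaged effect for the primary and the verified outcome, and a subject-specific effect for point prevalence abstinence at months 3 and 9. A reader who compares a secondary odds ratio with the primary's, or with the proportions observed in each arm, could conclude that the secondary effect is much stronger when only the scale has changed.

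**Working it through.** **Inputs from the SAP.** The model forms in 4.3.1 and 4.3.2; 926 participants randomised 1:1, so 463 per arm; planning rates of 3% and 9% (3.4). The SAP gives no participant SD, no within-person correlation, no persistence of abstinence between months 3 and 9, and no point prevalence rates. All of these are assumptions below.

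**Step 1: conditional against group-level odds ratio at a fixed SD.** With participant effect b ~ N(0, σ²), the rate in an arm is p = E[expit(α + b)]. Solve for α in each arm so that p equals the target rate. The conditional odds ratio is exp(α₁ − α₀). The 3% and 9% are the SAP's rates for continuous abstinence and serve only as an illustration; 10% and 20% are assumed.

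| σ | 3% vs 9% | 10% vs 20% |
|---|---|---|
| 0 (group level) | 3.20 | 2.25 |
| 1 | 3.45 | 2.50 |
| 2 | 4.54 | 3.28 |
| 3 | 6.82 | 4.68 |
| 4 | 10.87 | 6.91 |
| 5 | 17.83 | 10.38 |

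At σ = 1 the gap is at most 11% (2.50/2.25 = 1.11). At σ = 3 it is about two-fold (6.82/3.20 = 2.13).

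**Step 2: the site intercept alone.** The same calculation for the primary's structure at 3% vs 9% gives 3.22 at a site SD of 0.3 and 3.25 at 0.5, against 3.20. The mismatch comes from the participant term, not the site term.

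**Step 3: what SD the data would imply.** Let p be month-3 abstinence, s the share of month-3 abstainers still abstinent at month 9, and n the share of the others newly abstinent. Then month-9 abstinence is q = p·s + (1 − p)·n. For p = 15% and 25%, s = 0.5, n = 0.03:

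- q(control) = 0.15 × 0.5 + 0.85 × 0.03 = 0.1005
- q(VNP) = 0.25 × 0.5 + 0.75 × 0.03 = 0.1475
- group-level odds ratio at month 3 = (0.25/0.75)/(0.15/0.85) = 1.89
- group-level odds ratio at month 9 = (0.1475/0.8525)/(0.1005/0.8995) = 1.55

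The random-intercept logit with time, treatment and their interaction was then fitted by maximum likelihood (101-point Gauss-Hermite quadrature) to the expected month-3 by month-9 counts, 463 per arm. The site intercept and the priors were left out. Each odds ratio cell shows conditional vs group level, with the ratio in brackets.

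| p control, p VNP, s, n | fitted σ | month 3 | month 9 |
|---|---|---|---|
| 15%, 25%, 0.5, 0.03 | 4.16 | 5.13 vs 1.89 (2.7) | 2.82 vs 1.55 (1.8) |
| 15%, 25%, 0.6, 0.03 | 5.11 | 7.08 vs 1.89 (3.7) | 3.89 vs 1.60 (2.4) |
| 10%, 20%, 0.5, 0.03 | 4.04 | 6.93 vs 2.25 (3.1) | 3.24 vs 1.70 (1.9) |
| 12%, 22%, 0.5, 0.05 | 3.32 | 4.54 vs 2.07 (2.2) | 2.25 vs 1.51 (1.5) |
| 15%, 25%, 0.3, 0.05 | 2.19 | 2.77 vs 1.89 (1.5) | 1.50 vs 1.32 (1.1) |
| 15%, 25%, 0.2, 0.05 | 1.64 | 2.39 vs 1.89 (1.27) | 1.29 vs 1.23 (1.05) |

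**Step 4: the null.** If the arms have equal rates, α₁ = α₀ and both odds ratios equal 1. When there is an effect, the sign is the same on both scales.

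**The case against.** **The model is standard and a conditional odds ratio is a legitimate estimand.** This stands. The model form is not an error, the null and the direction are preserved, and nothing here shows an effect on the probability of direction or the Bayes factor. Raw proportions by arm, if shown, would reveal the actual size of a difference. The fault is that the plan attaches one description to two quantities and includes no step to bring them together.

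**The SAP does not commit to an odds ratio.** Section 4.2.6 leaves absolute or relative open. That is correct, so it should not be said that the SAP promises exponentiated coefficients. It does not settle the matter, however: an absolute difference is not a parameter of a logit model, and the SAP gives no derivation of one.

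**A reader might infer that the secondary effects will be far larger in every case.** The SAP does not support this. It gives neither the participant SD nor the persistence, and with low persistence the gap nearly closes, above all at month 9.

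**A reader might also infer that coding missing as not abstinent must inflate the SD, because about 40% would be zero at both times.** The SAP gives 40% attrition for month 9 only (3.4). People missing at both visits add constant zeros, which raises the SD. A month-3 abstainer lost by month 9 becomes a 1-then-0 pattern, which lowers persistence and works the other way. The net direction is not known.

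**Weak identification of the SD from two binary observations per person** is a fair worry, given the unstated prior scale. It has not been demonstrated: the fits above use expected counts, omit the planned prior and carry no uncertainty.

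**Conclusion.** The point holds for the binary secondary outcomes measured at months 3 and 9. Under the plan as written, their treatment parameter is subject-specific; if there is an effect, it lies further from the null than the odds ratio between the randomised groups and is not on the primary's scale. The inflation is about 1.05- to 1.5-fold when 20% to 30% of month-3 abstainers stay abstinent, and about 1.5- to 3.7-fold when 50% to 60% do, with the larger values at month 3. These ranges depend on assumed point prevalence rates, persistence and new abstinence, and come from maximum-likelihood fits rather than the planned Bayesian model. The matter affects the size and interpretation of secondary effects, not the validity of the trial's main conclusion. The primary and the biochemically verified outcome are unaffected.

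**What to change.** For every binary outcome measured at both months 3 and 9, amend 4.3.2 and 4.2.6 to do one of the following:

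1. Keep the planned model. For each posterior draw, average the predicted probability over the participant and site effects within each arm at each time. From those two probabilities, report the population-averaged risk difference and odds ratio with their credible intervals.
2. Fit months 3 and 9 separately with the primary's model (site intercept plus treatment).

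If the participant-intercept coefficient is shown at all, label it as conditional on the participant.

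The cost is a short post-processing step on draws that will exist anyway (or one extra fit per time point), plus the SAP wording. The reported odds ratios will be smaller, but they will agree with the observed proportions and can be read beside the primary.

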#### **4.4. Sensitivity analysis**

A series of sensitivity analysis will be performed assessing how robust the results are to:

- 1) missingness (see Missing Data section),
- 2) abstinence defined using stricter thresholds for CO ( $\leq 5$  ppm and  $\leq 3$  ppm),
- 3) adjusting for baseline characteristics that were potentially not well balanced between the groups at baseline.
- 4) the choice of prior for Bayesian analysis. A power prior (normal distribution) for the treatment effect using previously published data will be assessed. Non-informative priors for all other parameters will be used.

The primary outcome will be assessed for sensitivity to missingness by assuming missing at random (MAR) (Russel Standard will be used as the primary imputing method for the main analysis) and for the choice of prior. If evidence of the primary outcome treatment effect is shown, additional analysis by assuming missing not at random (MNAR) will be conducted using pattern mixture models (see Missing Data section).

Secondary outcomes will be assessed for sensitivity to missingness by assuming MAR, and if both the primary and secondary outcome show a treatment effect, additional analysis by assuming MNAR will be conducted using pattern mixture models (see Missing Data section).

#### **4.5. Missing Data**

It is anticipated that there will be two main mechanisms that will enable missing data will be observed in the data sources for the primary and secondary outcome: 1) participant that have not completed the follow-up CATI surveys (at 3 or 9-months) and are considered lost to

follow-up; and 2) participants that were successfully reached at follow-up; however, the outcome is missing. It is expected the first scenario is most likely.

The main analysis will be conducted in the intention to treat population. The primary method of imputing missing data will follow the recommendations of the Russel Standard, and assume those with missing data to be not abstinent.

A sensitivity analysis will be conducted under the missing at random assumption and, if evidence of a treatment effect is shown then missing not at random (MNAR). The analysis will be conducted using multiple imputation by chained equations with predictive mean matching models (PMM). PMM models will use analysis variables (treatment, site, time and outcomes) plus variables known to be predictors of abstinence (???) and any variables found to be predictive of missingness. Chisq or t-tests on baseline psychometrics will be used to assess association with missingness on the primary outcome to include in the PMM models. The number of imputations will be the higher of the percentage missing or 25 and 20 iterations will be used. The stability of the results will be explored through increasing the number of imputations. Pattern mixture models will be used to assess the sensitivity of the missing at random assumption. A tipping point approach will be used by varying our assumptions regarding the outcome proportion for those with missing data in the treatment group until a positive treatment effect is nullified. This sensitivity analysis will enable a better understanding of the variability of the missing data and will be used to assess the impact of missing on the outcomes of the study.

## 4.6. Statistical Software

The cleaning, coding, and analysis of the data sets will be completed using Statistical Analysis System (SAS) version 9.4 and R (R Foundation for Statistical Computing, Vienna, Austria. URL <https://www.R-project.org/>).

